## Sub-trial

All Adverse Events will be collected from first dose up to visit 6 (54 weeks), and recorded in the AE section of the eCRF.

## 10.1.2 Exemptions to reporting

The following adverse events, in the context of this trial, do not require expedited reporting on Serious Adverse Event (SAE) forms, unless they result in death.

- Elective medical or surgical procedures or social admissions
- Pre-existing disease or a condition present that was diagnosed before trial treatment that does not worsen

## 10.2 Recording and reporting SAEs, SARs AND SUSARs

All SAEs, except those defined as exempt above, and SUSARs occurring from first administration of trial drug up to the routine visit post-surveillance colonoscopy (visit 10 for the main trial; and visit 6 for the resveratrol sub-trial) or 14 days post cessation of trial treatment where this occurs earlier than protocolised, are subject to expedited reporting. This should be conducted in accordance with the Sponsor SOP for reporting SAEs and on the COLO-PREVENT SAE Report Form. Completed forms should be emailed to the Sponsor ([contact]) and Leicester CTU ([contact]) immediately and within 24 hours of the research staff becoming aware of the event. All SAEs will be reviewed and tracked by the Sponsor (or their delegate) until resolution. Monthly line listings of all SAEs are reviewed by the Director of Research and Development on a monthly basis. Please note: the 14 day safety monitoring period following last dose is greater than 5X half-lives of all trial drugs.

For each **SAEs / SUSARs** the following information will be collected:

- full details in medical terms and case description
- event duration (start and end dates, if applicable)
- action taken
- outcome
- seriousness criteria
- causality (i.e. relatedness to trial drug / investigation), in the opinion of the investigator
- whether the event would be considered expected or unexpected.

Any change of condition or other follow up information should be emailed to Sponsor and Leicester CTU as soon as it is available or at least within 24 hours of the information becoming available. Events will be followed up until the event has resolved or a final outcome has been reached.

IRAS: 1005142 Page **73** of **109** 

The causality and expectedness of the SAE should be assessed by the Investigator(s) or another delegated medic on the SAE form.

For participants on the main trial, section 4.8 of the SmPC for aspirin and metformin will be used to assess expectedness of events (known as the reference safety information).

For participants on the resveratrol sub-trial, section 8.0 of the IB for resveratrol will be used to assess expectedness of events (known as the reference safety information).

Any SAE assigned by the Investigator or delegate as being related to the allocated treatment and unexpected according to the approved reference safety information will be classified as a "SUSAR" and is subject to expedited reporting to the Competent Authority (the MHRA) and the REC. The Sponsor or delegate will liaise with the Principal Investigator and Chief Investigator to ensure that the relevant eSUSAR report is completed and submitted to the Competent Authority (the MHRA) within the required timeframes. The Sponsor will then submit the eSUSAR report and safety report to the REC. Fatal or life-threatening SUSARs must be reported within 7 days and all other SUSARs within 15 days. Follow up reports must be provided in a timely manner and as per the request of the Sponsor or delegate.

### 10.3 Responsibilities

## Principal Investigator (PI) (or delegate):

- 1. Checking for AEs and ARs at every visit following first administration of IMP
- 2. Using medical judgement in assigning seriousness, causality and expectedness using the Reference Safety Information approved for the trial.
- 3. Ensuring that all SAEs and SARs (including SUSARs) are recorded and reported to the Sponsor and Leicester CTU immediately and within 24 hours of becoming aware of the event and provide further follow-up information as soon as available.
- 4. Ensuring that AEs and ARs are recorded and reported to the Leicester CTU in line with the requirements of the protocol.

## Chief Investigator (CI) / delegate or independent clinical reviewer:

- 1. Clinical oversight of the safety of patients participating in the trial, including an ongoing review of the risk / benefit.
- 2. Using medical judgement in assigning seriousness, causality and expectedness of SAEs where it has not been possible to obtain local medical assessment.
- 3. Immediate review of all SUSARs.
- 4. Review of specific SAEs and SARs in accordance with the trial risk assessment and protocol.
- 5. Preparing the clinical sections and final sign off of the Development Safety Update Report (DSUR).

# Sponsor (or delegate):

IRAS: 1005142 Page **74** of **109** 

- 1. Central data collection and verification of AEs, ARs, SAEs, SARs and SUSARs according to the trial protocol.
- 2. Reporting safety information to the CI, delegate or independent clinical reviewer for the ongoing assessment of the risk / benefit.
- 3. Reporting safety information to the independent oversight committees identified for the trial (Data Monitoring Committee (DMC) and / or Trial Steering Committee (TSC)).
- 4. Expedited reporting of SUSARs to the Competent Authority (MHRA in UK) and REC within required timelines.
- 5. Notifying Investigators of SUSARs that occur within the trial.
- 6. Checking for (annually) and notifying PIs of updates to the Reference Safety Information for the trial.
- 7. Preparing standard tables and other relevant information for the DSUR in collaboration with the CI and ensuring timely submission to the MHRA and REC.

### Trial Steering Committee (TSC):

In accordance with the Trial Terms of Reference for the TSC, periodically reviewing safety data and liaising with the DMC regarding safety issues.

## Data Safety & Monitoring Committee (DMC):

In accordance with the Trial Terms of Reference for the DMC, periodically reviewing unblinded overall safety data to determine patterns and trends of events, or to identify safety issues, which would not be apparent on an individual case basis.

#### 10.4 Notification of deaths

Deaths will be reported to Leicester CTU and the Sponsor, where applicable in accordance with the SAE requirements described previously, and within 24 hours of the investigator becoming aware. A death notification CRF will be completed for all participants that die following randomisation up to the final visit.

## 10.5 Pregnancy reporting

Guidelines around pregnancy are detailed in section 8.10.

All pregnancies within the trial (either the trial participant or the participant's partner) should be reported to the Chief Investigator, the LCTU and the Sponsor using the relevant Pregnancy Reporting Form within 24 hours of site awareness.

Pregnancy is not considered an AE unless a negative or consequential outcome is recorded for the mother or child/foetus. If the outcome meets the serious criteria, this would be considered an SAE.

The pregnancy must be followed up to determine outcome (including premature termination) and status of mother and child in accordance with Sponsor and local reporting

IRAS: 1005142 Page **75** of **109** 

requirements and timelines. The relevant pregnancy PIS will be provided to the participant or partner and consent to follow up the pregnancy will be obtained.

Any SAE occurring in association with a pregnancy, brought to the investigator's attention after the participant has completed the trial, and considered by the investigator as possibly related to the trial treatment, must be promptly reported to sponsor in accordance with Sponsor and local reporting requirements and timelines.

#### 10.6 Overdose

The Sponsor and Leicester CTU should be informed about any overdoses of trial drug and the appropriate adverse event reporting should be followed.

#### Aspirin overdose

Should an aspirin overdose be suspected, the trial drug should be withheld and local guidance and pathways should be followed.

#### **Metformin overdose**

Participants should be urgently assessed in the event of an overdose and hospital admission considered. The management of metformin overdoses should be as per standard clinical care by the local team. The most effective way to remove lactate and metformin is haemodialysis.

## Resveratrol/placebo

The investigator should use clinical judgement in treating the symptoms of a suspected overdose.

## 10.7 Reporting urgent safety measures

If any urgent safety measures are taken the CI/Sponsor shall immediately and in any event no later than 3 days from the date the measures are taken, give written notice to the MHRA and the relevant REC of the measures taken and the circumstances giving rise to those measures.

Please refer to the following website for details on clinical trials safety reporting: http://www.mhra.gov.uk/Howweregulate/Medicines/Licensingofmedicines/Clinicaltrials/Safetyreporting-SUSARSandASRs/index.htm

# 10.8 The type and duration of the follow-up of participants after adverse reactions

Following an adverse reaction (AR) the participants will be followed-up for an appropriate length of time as dictated by the nature of AR and their clinical needs. ARs will continue to be recorded and reported for up to 14 days after the last dose of IMP has been administered. Any SUSAR will need to be reported to the Sponsor and Leicester CTU irrespective of how long after IMP administration the reaction has occurred until resolved.

IRAS: 1005142 Page **76** of **109** 

## 10.9 Development safety update reports

Within 60 days following the anniversary of the authorisation date for the trial, a Development Safety Update Reports (DSURs) will be sent by the Chief Investigator to the MHRA and the Main Research Ethics Committee. A copy of the report will also be sent to the trial Sponsor. The LCTU will prepare the DSUR report on behalf of the CI and submit to the Sponsor who retain responsibility for submitting to the Competent Authority (MHRA) within the specified time frame.

#### 11. STATISTICS AND DATA ANALYSIS

## 11.1 Sample size calculation

For all sample size calculations we have assumed a negative binomial distribution (12, 90), with over-dispersion of 2.0 and used equation from Cundill & Alexander (91). Replication of the sample size found was done using the NCSS PASS 16.1 software. We have designed COLO-PREVENT with recent changes to the BCSP at the forefront. Specifically, we have factored in changes to the surveillance guidelines, which mean high risk patients will have their first surveillance colonoscopy at 3 years instead of 12 months. Additionally, the risk classification has changed such that it is estimated the new high risk group is composed of individuals that previously fell under this category, plus a proportion (~50%) of the patients previously classed as intermediate risk who used to have their first surveillance colonoscopy at 3 years. A consequence of these changes is that real data do not yet exist on MPP for the new high risk group; therefore, we have made use of the most relevant data available and made a number of reasonable assumptions as described below.

For the main trial the primary analysis aims to show whether the combination of aspirin with metformin leads to clinically meaningful reduction in the MPP as compared to aspirin alone. Data from the aspirin arms of the SeAFOod trial (12) and 1st surveillance in the BCSP (2006 -2016, 1 year MPP for high risk patients and 3 year MPP for intermediate risk patients) have been provided ([name], personal communication). Assuming a MPP at 3 years in the untreated population of 1.2 polyps, this leads to a control MPP of 0.94 in the standard of care arm, after accounting for a 22% reduction in total MPP due to aspirin use, based on the SeAFOod data (12). This trial is powered to detect a reduction of 30% (0.66 vs 0.94) in the MPP of the combination arm, relative to aspirin alone. We estimate a sample size of 646 (323 per arm) would have 80% power at the 2-sided significance level of 5%. Allowing for 15% dropout at 3 years and crossover of 3% in each arm, the target sample size has been inflated to  $646/0.85 = 760^{\circ} - 1.13 = 862$  (431 per arm) individuals who will be randomised equally (1:1 ratio) to each treatment arm, with minimisation for BCSP Centre. We have predicted the dropout rate based on the 10% value reported for the one-year seAFOod trial (12) and have increased this figure to 15% due to the longer intervention period in COLOPREVENT; this rate is in line with previous aspirin polyp prevention trials that involved a ≥3 year follow-up (10). Crossover accounts for participants who have to stop taking metformin completely due to side effects, and also patients who are diagnosed with T2DM during the course of the trial and are prescribed metformin. Assuming a conservative but realistic acceptance and eligibility of 30% for the trial, a total of ~3200 high risk individuals need to be identified at screening colonoscopy.

IRAS: 1005142 Page **77** of **109** 

For the resveratrol signal-seeking phase II trial, comparing two doses of resveratrol against a placebo control group, the patients will be a combination of those taking aspirin and those not taking aspirin, so we have a used a pooled average MPP at 1 year from the aspirin groups in seAFOod and the untreated population from the BCSP (2006 -2016) data, and estimate the MPP in the control arm for this trial to be 1.2. As this is a signal-seeking trial, we will aim for a 1-sided 10% significance level and will not adjust for multiple testing due to the two active treatment arms. We aim for 80% power to ensure a high probability of detecting a Signal-Seeking reduction in MPP for this group of 30%, which will lead to a MPP of 0.84. We are aiming to recruit 477 patients (159 per arm) which includes a 10% drop out at 1 year. Therefore 477 individuals will be randomised equally (1:1:1 ratio) to the three treatment arms with minimisation by BCSP Centre and according to aspirin or metformin use, ensuring an even distribution across arms of these factors. Assuming a 50% acceptance and eligibility rate for this trial, a total of ~1200 high risk individuals will need to be identified at screening.

For both studies the total number of high risk individuals needed for screening is 4400, of whom we anticipate 75% will not be taking aspirin or metformin and so will be eligible for the main trial. We predict that the remaining 25% will be intolerant or already taking aspirin/metformin and would be offered entry into COLO-PREVENT Signal Seeking subtrial. Note that the overall predicted MPP value for the new HR group in the BCSP could be underestimated as we are using the one-year MPP for the previous high risk patients for three year MPP predictions, since data do not currently exist for recurrence at three years in this population. Furthermore, when factoring in the contribution from the previous intermediate-risk patients we are using the average three-year MPP for the whole group, whereas only a proportion of these patients will be incorporated into the new high risk classification. Once the new guidelines are fully implemented, after three years we will apply to the BCSP Research Advisory Committee to access the emerging data from the control BCSP patients to see how the real MPP value compares with our predicted value and make any adjustments to our sample sizes; the findings will be made available to the DMC.

The effect on clinical outcomes in the long term is important and all participants will be consented for additional follow-up (10 years) and clinical events will be ascertained through the BCSS, NCRAS, and other appropriate datasets.

### 11.2 Planned recruitment rate

We plan to exploit the legacy of the seAFOod trial utilising the infrastructure set up within the BCSP. We have been able to review the recruitment data from the trial to robustly confirm the feasibility of recruitment into COLO-PREVENT. Moreover, we have planned for an increased number of trial sites and with the efficient trial design can recruit patients into the COLOPREVENT sub-trial who are already taking/intolerant to aspirin or metformin. Excluding the 12-month run-in period, seAFOod recruited on average 16 patients per month (range 7-26) from 53 centres, which equates to 18% of the high risk patients screened for enrolment. A further 20% of this high risk group were excluded due to existing aspirin/NSAID use or aspirin intolerance; these patients would all be eligible for the COLO-PREVENT sub-trial. Therefore, with the wider eligibility, we realistically expect to recruit 30% of the high risk patients, and by increasing the number of sites to 60, we anticipate

IRAS: 1005142 Page **78** of **109** 

being able to recruit an average of 30 individuals per month once all the sites are open and recruiting to both trials.

As explained in Section 11.1 above, it is likely that our prediction of adenoma recurrence at 3 years for the new high risk group of patients under the updated BCSP criteria is an underestimate of the true value; this would mean our trial is overpowered. As 'real world' data become available for this new high risk group, we will conduct a formal review (at ~48 months) of adenoma recurrence (MPP) for control patients within the BCSP and compare to our predicted values. The findings from this review will be made available to the DMC.

## 11.3 Statistical analysis plan

**Statistical Analysis:** All statistical analyses will be carried out according to a detailed Statistical Analysis Plan (SAP), to be agreed by trial statisticians, the CI, and the TSC. The analysis will primarily follow an intention-to-treat (ITT) approach to the analysis i.e. participants will be analysed in the groups to which they were randomised and not treatment received. Additional analyses to evaluate the extent to which following the protocol is important will be pre-specified in the SAP e.g. per protocol and complier-average causal effects analyses.

## 11.3.1 Summary of baseline data and flow of patients

The flow of the patients in the trial will be described according to CONSORT guidelines for RCTs (92). The baseline characteristics will be summarised by randomised group without formal statistical comparison.

### 11.3.2 Primary outcome analysis

The primary outcome will be analysed using a generalised linear model to estimate incident rate ratios between randomised groups, assuming a negative binomial distribution, MPP as the outcome variable and randomisation group as the explanatory variable. Results of comparative analyses will present point estimates, 95% confidence interval and P-value.

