#### 7.3 Randomisation

**For the main trial**, participants will be randomised in a 1:1 ratio to aspirin or aspirin + metformin, with minimisation by BCSP centre. The main trial is open-label, so the research team and participants will be aware of their treatment assignment. However, we will minimise potential bias at the surveillance colonoscopy, by asking participants and the research team not to reveal their treatment assignment to endoscopy staff.

**For the resveratrol sub-trial**, two doses of resveratrol (5mg and 1g) are compared against a placebo control group. Participants will be randomised equally in a 1:1:1 ratio to the three treatment arms and according to aspirin or metformin use, ensuring an even distribution across arms of these factors. The sub-trial will be double-blinded, so the research team and participants will not be aware of treatment assignment.

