## 11.3.3 Secondary outcome analysis

All secondary end-points will be analysed using the ITT population, with the exception of adverse events, for which we will analyse the safety population, consisting of all participants who received at least one dose of trial medication. Data on adverse events will be tabulated by randomised group. Logistic regression will be used to estimate odds ratios between randomised groups for polyp detection rate, polyp subtype and location. The relative recurrence of 'advanced' polyp detected at the first BCSP surveillance colonoscopy will be analysed using log-binomial regression model with robust standard errors to estimate the log relative risk. The region of the colorectum where polyps are detected at the first BCSP surveillance colonoscopy will be explored, possibly using a negative binomial random effects model with bivariate response (corresponding to polyp counts in the left and right colon) in which treatment and a baseline polyp count will be independent variables together with the random intercepts corresponding to patient and BCSP centre.

IRAS: 1005142 Page **79** of **109** 

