## 11.5 Adjusted analysis

A per-protocol analysis will be conducted as a sensitivity analysis, where the per-protocol population consists of all randomised participants who were not deemed to have a protocol violation. Additionally, some BCSP centres consist of multiple hospitals (sites), therefore an additional sensitivity analysis will be conducted in which both BCSP centre and site will be treated as random effects in a multi-level model. Drug adherence will be monitored and if adherence is considered to be poor, alternative analysis methods such as Complier Average Causal Effect (CACE) analysis will be considered.

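### The primary model adjusts for nothing: it is valid and has its planned power, but gives up precision that the index polyp count and the minimisation factors could supply

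*Protocol*

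**What the plan says.** Section 11.3.2 specifies a generalised linear model with a negative binomial distribution, "MPP as the outcome variable and randomisation group as the explanatory variable". No other term is listed.

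The factors used in allocation are these:
- **Main trial (Section 7.3):** "randomised in a 1:1 ratio to aspirin or aspirin + metformin, with minimisation by BCSP centre".
- **Sub-trial (Section 11.1):** "minimisation by BCSP Centre and according to aspirin or metformin use, ensuring an even distribution across arms of these factors".

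The omitted variables appear elsewhere in the analysis sections:
- **Centre:** Section 11.5 has a sensitivity analysis in which "both BCSP centre and site will be treated as random effects in a multi-level model".
- **Baseline polyp count and centre:** Section 11.3.3 describes a possible bivariate model for left- and right-sided counts in which "treatment and a baseline polyp count will be independent variables", with random intercepts for patient and centre.
- **Aspirin or metformin use:** named in no stated efficacy model.

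**The concern.** The protocol balances allocation on certain factors and then leaves them out of its main model. It names a baseline polyp count for an exploratory analysis but not for the one that decides the trial. The index count is a natural predictor of the surveillance count. Eligibility under Section 6.1 runs from a single large non-pedunculated polyp to five or more premalignant polyps, and Section 1.1 says that lesions found after polypectomy include ones missed at the index procedure.

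Precision is what is at stake. Differences between people that a known baseline variable could explain stay in the error term. With a log link and no treatment interaction, adjusting for a covariate that is independent of treatment leaves the rate ratio unchanged, so the gain does not alter the quantity being estimated.

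**Working it through.** **Inputs from Section 11.1.** Over-dispersion 2.0. Main trial: MPP 0.94 v 0.66, two-sided 5%, 80% power, 323 per arm. Sub-trial: MPP 1.2 v 0.84, one-sided 10%, 80% power, 159 per arm including 10% dropout.

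**Step 1: reproduce the plan.** Read over-dispersion as variance/mean = 2:

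n per arm = (z_α + z_β)² × 2 × (1/μ₁ + 1/μ₂) / [ln(μ₁/μ₂)]²

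- Main trial: (1.960 + 0.842)² × 2 × (1/0.94 + 1/0.66) / 0.35364² = 7.849 × 5.158 / 0.12506 = 323.7, against 323 stated.
- Sub-trial: (1.282 + 0.842)² × 2 × (1/1.2 + 1/0.84) / [ln(1.2/0.84)]² = 143.4. Dividing by 0.9 gives 159.4, against 159 stated.

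Other readings do not match the main-trial figure: a shape parameter k = 2 gives 225 per arm, and a dispersion 1/k = 2 gives 413. Both trials are therefore sized on the unadjusted comparison with variance/mean 2.

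**Step 2: effect of adjustment, main trial.** With variance/mean 2, half the variance of the log rate ratio is Poisson noise (1/0.94 + 1/0.66 = 2.579) and half is between-person dispersion (also 2.579). Covariates can reduce only the second half. If they explain a fraction f of it:

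Var = [2.579 + (1 − f) × 2.579] / 323

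Power = Φ(0.35364/√Var − 1.960)

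| f (assumed) | Fall in variance | SE | Power at 323 per arm | n per arm for 80% |
|---|---|---|---|---|
| 0 | 0% | 0.1264 | 79.9% | 324 |
| 10% | 5% | 0.1232 | 81.9% | 308 |
| 20% | 10% | 0.1199 | 83.9% | 292 |
| 30% | 15% | 0.1165 | 85.9% | 276 |

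A single dispersion parameter of 1/0.94 for both arms is a different design. It needs only about 295 per arm and already has 83.4% power at 323, so it should not be anchored at the plan's 80%.

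**Step 3: simulation of the same design.** The set-up was 646 participants, 60 centres, minimisation by centre, variance/mean about 2 and 2,500 runs per scenario. Power for arm only v arm plus index count was:
- 80.6% v 82.1% (index-count effect 0.3 per SD on the log scale, between-centre SD 0.2)
- 82.5% v 86.6% (0.5, 0.2)
- 83.2% v 87.9% (0.5, 0.4)

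These effect sizes are also assumptions.

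**Step 4: do the standard errors suffer?**
- **Centre.** Its share of the variance is about (e^(SD²) − 1)/2.579: 1.6% at SD 0.2 and 6.7% at SD 0.4. In the simulations, arm-only type I error was 5.1% to 5.7%. The Monte Carlo standard error is √(0.05 × 0.95/2,500) = 0.4 points, so there is no sign of conservatism.
- **Aspirin use, sub-trial.** Section 11.1 takes a 22% reduction from aspirin. With user share p, the share of per-person variance is about p(1 − p) × (ln 0.78)² × 1.2²/2.4. This is 0.7% at p = 25% or 75%, and 0.9% at p = 50% (p is assumed). With perfect balance, the one-sided 10% test would run at 1 − Φ(1.2816/√(1 − 0.0093)) = 9.9%.
- **Metformin use.** The documents give no effect on MPP for this population from which to calculate a share.

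**The case against.** The strongest reply is that nothing is broken. The unadjusted model matches the basis of the sample size and delivers its 80%. Section 11.2 even expects the trial to be overpowered if recurrence has been underestimated. All of this stands. A reader might infer that the trial is underpowered as written, and the documents do not support that.

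A reader might also infer that omitting the minimisation factors makes the standard errors too large and the test conservative. That is the right direction in theory, but Step 4 shows no sign of it for centre, the main trial's only minimisation factor, and a negligible amount for aspirin use. Nor is centre ignored altogether, since Section 11.5 includes it in a sensitivity analysis. What is in question there is which model is primary.

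The size of the gain does rest on assumption. No document says how well the index count predicts the surveillance count, and eligibility rules that restrict its range could weaken it.

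Finally, Section 11.3 refers the analyses to a detailed SAP, and Section 11.3.4 speaks of adjustments in line with the main trial analyses, so adjustment may be contemplated there. This carries less weight. Section 11.3.2 states the explanatory variable of the primary model, so a SAP that made an adjusted model primary would depart from the protocol.

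**Conclusion.** The point holds as one of efficiency, not validity. Section 11.3.2 states a treatment-only primary model and leaves out data the trial will already hold. The loss is forgone precision: about 2, 4 or 6 points of power above 80% if covariates explain 10%, 20% or 30% of the between-person dispersion. That range is assumed. The calculation also rests on reading over-dispersion as variance/mean 2.0, which the reproduced sample sizes support. Most of any gain would come from the index count; centre and aspirin use are likely to add little. The change is worth making because it costs almost nothing, but the planned analysis would still give a sound answer without it.

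**What to change.** Amend Section 11.3.2, and the SAP to match, before any comparative outcome data are seen. The main trial is open-label, so adjustment added later could look data-driven.

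- **Primary model:** negative binomial regression of each participant's polyp count on treatment, log(1 + index polyp count) and a random intercept for BCSP centre. In the sub-trial, add aspirin use and metformin use.
- **Index count:** define it as all premalignant polyps over the completed qualifying screening episode, including site checks for patients with piecemeal resection of a large non-pedunculated polyp. Section 1.1 allows an episode to contain several procedures, so the definition has to be written down.
- **Sensitivity analysis:** keep the treatment-only model.
- **Non-convergence:** keep the fixed covariates and move to a prespecified simpler treatment of centre, for example GEE or robust standard errors clustered by centre.

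The cost is about one paragraph of text, with no extra patients and no new data. The small downside is the need for that fallback, because there are about 60 small centres.
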